12.8.2. Secondary Endpoints and Methods

12.8.2.1. Overall Survival (OS) and Survival Rate at Landmark Points

Patients will be followed for survival status until end of study.

OS is defined as the time from date of randomization until date of death due to any cause. Patients who are known to be alive or whose survival status is unknown will be censored at the date last known to be alive. Patients who are completely lost to follow-up for survival will be censored at randomization date.

The analysis methods for overall survival will be similar to those described for PFS.

In addition, survival rate at landmark points will be summarized for each treatment arm using Kaplan-Meier point estimates and compared using the standard normal Z test.

12.8.2.2. Overall Response Rate

Overall response rate (ORR) is defined as the proportion of patients who achieve a CR, CRi, nPR, or PR over the course of the study as evaluated by the IRC using IWCLL 2008 criteria. Patients who do not have any post-baseline response assessment will be considered as non-responders. A Cochran-Mantel-Haenszel chi-square test, stratified by the two randomization stratification factors, will be used to compare the two treatment arms.

12.8.2.3. Patient-Reported Outcome (PRO) Measures

PRO as measured by FACiT-Fatigue will be summarized as the change in scores from baseline to each assessment.

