	
Descriptive statistics for change in scores from baseline to each assessment will be summarized for the PROs assessed by the FACiT-Fatigue. Time to hematological improvement will be compared using unstratified log rank test. Percentage of patients achieving hematological improvement will be compared using the chi-square test.
 
Exploratory Efficacy Analysis:
 
PFS and ORR as determined by the Investigator will be summarized and analyzed similarly to PFS and ORR as determined by the IRC. Percentage of patients achieving improvement/or resolution in disease-related symptoms will be compared using chi-square test.
 
Descriptive statistics for change in scores from baseline to each assessment will be summarized for the PROs assessed by EORTC QLQ-C30 and EQ-5D-5L.
 
Descriptive statistics will be provided for parameters collected for medical resource utilization associated with the therapy.
 
Safety Analysis:
 
Detailed tabulations of safety data (adverse events [AEs] and clinical laboratory tests) will be provided for all patients receiving the study drug. The number and percent of patients with treatment-emergent AEs will be summarized. Summary of other safety parameters by treatment group will be provided where appropriate.

Interim Analysis	
One interim analysis using the Lan-DeMets alpha spending function based on O'Brien-Fleming boundary for both superiority and futility (non-binding) will be conducted after observing approximately 117 PFS events. Futility will be evaluated by a one-sided test. The DMC will review and evaluate efficacy and safety results.

Sample Size Determination	
With the agreement from the European (Rapporteur and Co-Rapporteurs) and US Health Authorities, the overall two-sided significance level for this study is revised from 0.01 to 0.05. Given this revision in overall significance level, 176 PFS events provides approximately 90% power to detect the target hazard ratio of 0.6 based on a log-rank test and a two-sided overall significance level of 0.05 adjusted for one planned interim analysis.

TABLE OF CONTENTS

PROTOCOL APPROVAL PAGE	2
SYNOPSIS.....	3
TABLE OF CONTENTS	9
LIST OF TABLES	14
LIST OF FIGURES	15
LIST OF APPENDICES	15
LIST OF ABBREVIATIONS AND DEFINITIONS	16
1. INTRODUCTION.....	20
1.1. Ibrutinib.....	20
1.1.1. Mechanism of Action of Ibrutinib.....	21
1.1.2. Cellular Selectivity of Ibrutinib.....	21
1.2. Summary of Nonclinical Data	22

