3.2. Secondary Objectives

To compare between the two treatment groups in terms of:

Efficacy

- To evaluate overall survival (OS)
- To evaluate IRC-assessed overall response rate (ORR) per IWCLL 2008 criteria
- To evaluate patient-reported outcome (PRO) by the Functional Assessment of Chronic Illness Therapy-Fatigue (FACiT-Fatigue)
- To evaluate hematological improvement

Safety

To evaluate the safety and tolerability of ibrutinib compared to ofatumumab

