11.2. Secondary

Efficacy

To compare between the two treatment groups in terms of:

- OS
- Overall response rate (ORR) is defined as the proportion of patients who achieve complete response (CR), complete response with incomplete bone marrow recovery (CRi), nodular partial response (nPR), or partial response (PR) per IWCLL 2008 criteria over the course of the study as evaluated by an IRC
- Patient reported outcome (PRO) as measured by the FACiT-Fatigue.
 - The efficacy measure for the FACiT-Fatigue will be the change in scores from baseline to each assessment.
- Hematological improvement in the subset of patients with cytopenia(s) at baseline assessed by time to improvement and percentage of patients with improvement

Safety

- To compare the safety and tolerability between the two treatment groups

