12.4. Interim Analysis

A pre-specified interim analysis for both superiority and futility (non-binding) will be performed after approximately 117 IRC confirmed PFS events are reported. Futility will be evaluated by a one-sided test. One-hundred and seventeen (117) PFS events correspond to 66.5% of the revised planned number of PFS events (176) for the final analysis. Lan-DeMets spending function with O'Brien-Fleming boundary will be used as an early stopping guidance (O'Brien 1979). At the interim analysis, the alpha spending for PFS will be determined based on the actual information fraction using O'Brien-Fleming boundary. Significance level for all secondary endpoints except OS will be adjusted with the same significance level as for PFS at the interim analysis. The two sided significance level for OS will be 0.03 at the interim analysis. The independent DMC will review the interim PFS analysis results and make a recommendation accordingly. Details regarding interim efficacy analysis will be described in the DMC charter and the SAP.

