12.5. Final Analysis

The final analysis for the PFS will be conducted after approximately 176 PFS events are confirmed by the IRC. The two-sided significance level for the final analysis for primary and all secondary endpoints will be adjusted to account for interim alpha spending so the overall two-sided significance level for the study will be preserved at 0.05.

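### FACiT-Fatigue is listed as a between-arm secondary endpoint, but the protocol and supplied SAP specify only descriptive by-visit change scores and no between-arm estimate

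*Protocol*

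**What the plan says.** Protocol 3.2 introduces the secondary objectives with "To compare between the two treatment groups in terms of", and FACiT-Fatigue is one of the efficacy items below that line. Section 11.2 repeats the framing, lists "Patient reported outcome (PRO) as measured by the FACiT-Fatigue", and adds: "The efficacy measure for the FACiT-Fatigue will be the change in scores from baseline to each assessment". The synopsis endpoint list is framed the same way.

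The analysis is thinner. Section 12.8.2.3 reads in full: "PRO as measured by FACiT-Fatigue will be summarized as the change in scores from baseline to each assessment". The synopsis agrees: "Descriptive statistics for change in scores from baseline to each assessment will be summarized for the PROs assessed by the FACiT-Fatigue".

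The other secondary efficacy endpoints have named comparisons. OS follows the PFS methods (12.8.2.1). For ORR, a stratified Cochran-Mantel-Haenszel test "will be used to compare the two treatment arms" (12.8.2.2). Hematological improvement has a log-rank and a chi-square test (12.8.2.4).

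The significance-level rules do not exempt FACiT-Fatigue. Section 12.4 states: "Significance level for all secondary endpoints except OS will be adjusted with the same significance level as for PFS at the interim analysis". Section 12.5 says the "two-sided significance level for the final analysis for primary and all secondary endpoints will be adjusted to account for interim alpha spending".

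Protocol 12 defers analysis detail to the SAP. Table 1 of the supplied SAP covers PFS, OS, ORR, hemoglobin and platelets, and no patient-reported outcome. SAP Section 1 limits that document to the final analysis.

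**The concern.** A secondary endpoint meant for comparing arms should come with a defined contrast. Here there is no between-arm estimate, confidence interval, primary time point, baseline covariate or missing-data rule. FACiT-Fatigue has a significance level but no test to apply it to.

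Two things are at stake. First, a reader who compares the by-visit means is comparing whoever completed the form at that visit. Scheduled collection largely ends at progression, and the trial is designed on the expectation that progression differs by arm, so the completers may be selected differently in each arm. This sits poorly with Protocol 12.6.1, which puts all efficacy analyses on the ITT population. Second, if a between-arm difference is taken from raw change scores, the screening score is used only by subtraction. That is less precise than adjusting for it.

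**Working it through.** The documents give no sample size, SD, correlation or power for FACiT-Fatigue, so there is no figure on this endpoint to reproduce. The only power statement concerns PFS.

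**1. When scores are collected**
- Screening (Protocol 7.3.1), then weeks 4, 8, 12, 16, 20 and 24 on treatment (7.3.2.5), then every 12 weeks (7.3.2.6).
- End-of-treatment visit, 30 days after stopping (7.3.2.8).
- After stopping treatment, every 12 weeks until progression or study closure (7.3.3.1).
- None in the post-progression list (7.3.3.2), and none in Appendix M for controls who move to ibrutinib.
- Progression requires treatment to stop (10.1).

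So scheduled collection ends with progression, apart from the end-of-treatment score.

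**2. How many might have progressed or died by week 24**

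Week 24 is 168/30.4 = 5.52 months. Assuming exponential PFS with control median m, the proportion is 1 − exp(−ln 2 × 5.52/m). The value 5.8 is the midpoint of the 5.7 and 5.9 months cited in Protocol 2.2; the other medians are assumptions.

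| Control median (months) | Controls progressed or dead by week 24 |
|---|---|
| 5.8 | 48% |
| 8 | 38% |
| 10 | 32% |
| 12 | 27% |

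At the design hazard ratio of 0.6 (12.3), the ibrutinib proportion is 1 − (control proportion event-free)^0.6. That gives 1 − 0.517^0.6 = 33% against 48%, and 1 − 0.727^0.6 = 17% against 27%. Using instead the 12-month PFS of 88% cited in Protocol 1.3.2.1 for ibrutinib 420 mg, it is 1 − 0.88^(5.52/12) = 6%.

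**3. Progressed is not the same as missing**

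Response evaluations are 12-weekly and coincide with standard visits (7.3.2.7), and questionnaires are completed before other procedures (7.1.13). A patient whose progression is found at week 24 can therefore still give a week-24 score. If progression were found only at scheduled evaluations, those already lost to it would be the ones progressed or dead by week 12 (2.76 months), plus deaths between weeks 12 and 24. The week-12 part is 1 − exp(−ln 2 × 2.76/5.8) = 28% of controls at a median of 5.8 months and 1 − exp(−ln 2 × 2.76/12) = 15% at 12 months.

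**4. Precision of raw change against baseline adjustment**

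Let σ² be a common variance at baseline and follow-up, and ρ their correlation. Then Var(change) = 2σ²(1 − ρ), Var(baseline-adjusted) = σ²(1 − ρ²), and the ratio is (1 + ρ)/2.

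| Assumed ρ | Var(change)/σ² | Var(adjusted)/σ² | Ratio | Variance cut | Equivalent extra patients (1/ratio − 1) |
|---|---|---|---|---|---|
| 0.3 | 1.40 | 0.91 | 0.65 | 35% | 54% |
| 0.5 | 1.00 | 0.75 | 0.75 | 25% | 33% |
| 0.7 | 0.60 | 0.51 | 0.85 | 15% | 18% |

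For ρ = 0.5, 175 per arm, complete data and an assumed true difference of 0.3 SD, power at two-sided 0.05 rises from 80.1% to 90.0%.

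**5. Why one time point should be named**

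Testing each of the six visits to week 24 at 0.05 would give a familywise error of 1 − 0.95⁶ = 26% if the visits were independent, and less under positive correlation.

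**The case against.** The best defence is that FACiT-Fatigue was meant to be descriptive. The same lists promise a comparison of safety, which is then analyzed by tabulation (Protocol 12.9). The synopsis and 12.8.2.3 agree with each other. SAP Section 1 names only OS and ORR as key secondary endpoints, and restraint with a patient-reported outcome in an open-label trial is reasonable. This is a fair reading, but it does not explain why 12.4 and 12.5 give the endpoint a significance level, or why the other secondary efficacy endpoints have named tests. If descriptive was the intent, the protocol should say so.

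A reader might infer that no comparison was ever planned, that the sponsor dropped the endpoint, or that the trial cannot answer its fatigue question. The documents do not support this. Protocol 12 and 12.4 refer to an SAP, the December 2013 interim became the primary analysis (SAP Section 1), and an SAP for that analysis was not supplied. The supplied one covers the final analysis of a November 2018 extract.

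A reader might also infer that about half the control arm lacks week-24 scores. The 5.8-month median comes from fludarabine-refractory patients (Protocol 2.2), whereas Protocol 5.1 also admits patients on other grounds such as age, comorbidity or 17p deletion. Not everyone who progresses loses the week-24 score, and an end-of-treatment score is scheduled.

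It also stands that the precision gain matters only if a between-arm estimate is made, and that there is no stated power target for it to rescue.

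**Conclusion.** The point holds in limited form. The protocol and the supplied SAP specify no between-arm analysis for an endpoint that the protocol says will be compared between arms, and by-visit means after progression begins may contrast differently selected patients. The direction and size of any resulting bias cannot be read from the documents. The 27% to 48% range rests on exponential PFS and assumed control medians, and describes progression or death rather than missing scores.

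The precision result is firmer in direction than in size. With equal variances the ratio (1 + ρ)/2 is below 1 for any ρ below 1; the 15% to 35% cut depends on assumed correlations of 0.7 to 0.3.

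A mixed model should not be taken as a cure for progression-related dropout. It uses earlier scores to inform later visits under missing-at-random, which lessens the problem but does not remove it. The primary PFS conclusion is unaffected.

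**What to change.** Specify, in the ITT population, a mixed model for repeated measures on FACiT-Fatigue over weeks 4 to 24. Include arm, visit, arm-by-visit, baseline score, baseline-by-visit and the two randomization stratification factors. Report the week-24 between-arm difference with its 95% CI and keep the by-visit summaries as description. State visit windows for patients who stop treatment before week 24, since their scores then follow the end-of-treatment and 12-weekly schedule.

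Add a sensitivity analysis for scores missing after progression or death. One option is to shift imputed post-progression scores toward worse fatigue in steps until the conclusion changes, with a stated rule for deaths. If a p-value is to be claimed, give the endpoint a place in the secondary testing order. Unless a plan for the primary analysis already contained this model, label it as added after the interim results.

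If the sponsor does not want a comparison, the minimum is to label FACiT-Fatigue descriptive in 3.2 and 11.2 and exempt it from the significance-level statements in 12.4 and 12.5.

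The cost is one model and one sensitivity analysis on data already scheduled for collection. The downsides are reliance on missing-at-random for the main model and open-label reporting bias, which no adjustment removes.

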12.8.2.4. Hematological Improvements

In the subset of patients with cytopenia(s) at baseline (Hgb ≤ 11 g/dL, platelets $\leq 100,000/\mu\text{L}$, or ANC $\leq 1500/\mu\text{L}$), time to sustained improvement and percentage of patients with sustained hematological improvement will be measured. Sustained hematological improvement is defined as improvement in cytopenia by $\geq 50\%$, or Hgb > 11 g/dL, ANC $> 1500/\mu\text{L}$, platelets $> 100,000/\mu\text{L}$ with the duration of improvement lasting for at least 2 months without blood transfusion or growth factors.

- Time to sustained improvement in blood count will be compared using unstratified log rank test. The distribution of the time to sustained improvement will be summarized using Kaplan-Meier estimates.
- Percentage of patients with sustained improvement will be compared using χ^2 test.

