2.2. Selection of Ofatumumab as Comparator

Ofatumumab is a fully humanized type I anti-CD20 monoclonal antibody. *In vitro*, it mediates complement dependent cytotoxicity (CDC) against rituximab-resistant Raji cells and CLL cells with low expression of CD20. It appears to have greater potency in CDC than rituximab, as well as a slower off-rate and more stable CD20 binding ([Teeling 2004](#)). Additionally, it appears to bind a different epitope of CD20 than rituximab ([Teeling 2006](#)) and has demonstrated clinical activity that is independent of prior treatment with rituximab ([Wierda 2011](#)). A Phase 1/2 study of ofatumumab in relapsed/refractory CLL patients demonstrated that it is generally well-tolerated, even at high doses, and is active, with an ORR of approximately 50%. Infusion-related AEs are similar to those reported with rituximab and decrease following the first infusion ([Coiffier 2008](#)) of ofatumumab. Ofatumumab was evaluated in patients with fludarabine- and alemtuzumab-refractory (double refractory [DR]) and bulky fludarabine-refractory (BFR) CLL in a seminal study of 138 patients who have received treatment for CLL/SLL. Patients received 8 weekly infusions of ofatumumab followed by 4 monthly infusions over a 24-week period, receiving 300 mg as the first dose and 2000 mg for all doses thereafter ([Wierda 2010](#)). The ORR was 58% in the DR CLL group and 47% in the BFR CLL group with median PFS of 5.7 months and 5.9 months, and overall survival (OS) of 13.7 months and 15.4 months, for the two groups respectively. This data led to FDA (Food and Drug Administration) and EMA (European Medicines Agency) approval of ofatumumab in CLL in patients refractory to fludarabine and alemtuzumab. Currently NCCN NHL 2012 guidelines and European Society

for Medical Oncology (ESMO) guidelines support the use of ofatumumab in patients who have received treatment for CLL/SLL (NCCN 2012; Eichhorst 2011). The most common AEs for ofatumumab are infusion reactions, neutropenia, pneumonia, fevers, cough, and diarrhea. For more information on ofatumumab, please refer to the package insert.

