7.3.3. Follow-up Phase

7.3.3.1. Post-treatment Phase

After discontinuation of treatment, the following assessments will be performed every 12 weeks (± 7 days) until disease progression or study closure, whichever is earlier:

- Subsequent anticancer therapies
- Physical examination and ECOG performance status
- Disease-related symptoms (no longer required per Amendment 5)
- MRU (no longer required per Amendment 5)
- PRO assessments
- Hematology
- Serum immunoglobulins and β_2 -microglobulin
- T/B/NK cells
- Flow cytometry-based immunophenotype assays
- Predictive biomarkers and mechanisms of resistance

Prior to disease progression, response assessment (including CT, CBC and PE) need to be continued on a calendar schedule even if the patient receives subsequent anticancer therapy.

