7.3.3.2. Post-disease Progression Phase

Once patient progresses, the following assessments will be assessed every 12 weeks until death, withdrawal by patient, lost to follow-up, or study terminated by Sponsor, whichever comes first.

- Subsequent anticancer therapies
- MRU (no longer required per Amendment 5)
- Survival status

- Occurrence of any additional malignancy
- Occurrence of transformation to a more aggressive histology (Richter's transformation)

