12.6. Analysis Populations

12.6.1. Intent-to-Treat (ITT) Population

The ITT population is defined as all patients who were randomized. All efficacy analysis will be performed using the ITT population and patients in the ITT population will be analyzed as randomized. In addition, ITT population will be used to summarize demographics, and baseline and disease characteristics.

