- e. CBC should be performed weekly for the first 4 weeks

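### Protocol 12.8.2.4 summarises time to sustained haematological improvement by Kaplan-Meier without saying how death is handled; if deaths are censored, the curve overstates the probability of improvement in both arms

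*Protocol*

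**What the plan says.** Hematological improvement in patients with a baseline cytopenia is a secondary endpoint (Protocol 11.2), measured by time to improvement and by percentage improved. Protocol 12.8.2.4 requires the improvement to last at least 2 months without transfusion or growth factors, and plans:

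- Time to improvement, tested: "Time to sustained improvement in blood count will be compared using unstratified log rank test".
- Time to improvement, described: "The distribution of the time to sustained improvement will be summarized using Kaplan-Meier estimates".
- Share improved, a separate item: "Percentage of patients with sustained improvement will be compared using" a chi-square test.

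The section has no censoring rule, whereas PFS and OS have theirs in 12.8.1 and 12.8.2.1. Protocol 12.6.1 sets the population: "All efficacy analysis will be performed using the ITT population and patients in the ITT population will be analyzed as randomized".

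On when blood counts are taken:

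- After treatment stops (7.3.3.1, which lists hematology): "the following assessments will be performed every 12 weeks (± 7 days) until disease progression or study closure, whichever is earlier".
- After progression (7.3.3.2): "Once patient progresses, the following assessments will be assessed every 12 weeks until death". The list that follows contains no hematology.
- For ofatumumab patients who move to next-line ibrutinib, Appendix M schedules hematology every 4 weeks for 24 weeks and then every 12 weeks. Its note e adds: "CBC should be performed weekly for the first 4 weeks".

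SAP section 4, Table 1 (final analysis) has only proportions with sustained hemoglobin or platelet improvement, tested by chi-square. It has no time-to-improvement row.

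**The concern.** A Kaplan-Meier curve that censors deaths treats the dead as if they would have gone on to improve at the same rate as those still under observation. One minus that curve describes a setting in which nobody dies. It does not estimate the share of patients who have improved by a given month, which is how such a curve is normally read. Any median or landmark value taken from it inherits the error.

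Two results for the same endpoint would also disagree: the curve would climb above the raw percentage improved, and the plan does not explain why. Because competing events may be more frequent in one arm, the visual contrast between the curves can be distorted as well.

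**Working it through.** **Plan's own figure.** The documents give no improvement rate, number of cytopenic patients or expected result for this endpoint, so there is nothing to reproduce. What follows is illustrative.

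**Formulas.** Let a be the monthly hazard of improvement and c that of the competing event, both constant.

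- One minus Kaplan-Meier, competing events censored: 1 − exp(−a·t)
- Cumulative incidence: a/(a+c) × [1 − exp(−(a+c)·t)]

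**Step 1: death only, control arm, t = 12 months.** Protocol 2.2 cites "overall survival (OS) of 13.7 months and 15.4 months" for ofatumumab in two refractory groups. Taking 14.5 months, c = ln 2/14.5 = 0.0478. Set a so that one minus Kaplan-Meier is 30, 45 or 60% (assumed range).

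| 1 − KM | a | a/(a+c) | 1 − exp(−12(a+c)) | Cumulative incidence | Excess (points) |
|---|---|---|---|---|---|
| 30% | 0.0297 | 0.383 | 0.606 | 23% | 7 |
| 45% | 0.0498 | 0.510 | 0.690 | 35% | 10 |
| 60% | 0.0764 | 0.615 | 0.775 | 48% | 12 |

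Using the two cited medians separately changes little. At a = 0.05, one minus Kaplan-Meier is 45.1%, against a cumulative incidence of 34.8% (median 13.7) or 35.8% (median 15.4).

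The median is affected too. In the 30% row the Kaplan-Meier median is ln 2/0.0297 = 23.3 months. The cumulative incidence levels off at a/(a+c) = 38%, so half the patients never improve.

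**Step 2: progression or death as the competing event.** This applies only if improvement after progression is ruled out. Protocol 2.2 gives ofatumumab median PFS of 5.7 and 5.9 months; taking 5.8, c = ln 2/5.8 = 0.1195. For ibrutinib there are two possible proxies:

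- design hazard ratio 0.6 (Protocol 12.3): c = 0.6 × 0.1195 = 0.0717
- 12-month PFS of 88% in the 420 mg cohort (Protocol 1.3.2.1): c = −ln(0.88)/12 = 0.0107

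At 12 months:

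| Arm and assumption | a | 1 − KM | Cumulative incidence | Excess (points) |
|---|---|---|---|---|
| Ofatumumab | 0.05 | 45.1% | 25.6% | 19.5 |
| Ibrutinib, HR 0.6 | 0.05 | 45.1% | 31.5% | 13.6 |
| Ibrutinib, 88% PFS | 0.05 | 45.1% | 42.6% | 2.5 |
| Ofatumumab | 0.02 | 21.3% | 11.6% | 9.7 |
| Ibrutinib, HR 0.6 | 0.08 | 61.7% | 44.2% | 17.5 |
| Ibrutinib, 88% PFS | 0.08 | 61.7% | 58.5% | 3.2 |

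With improvement hazards of 0.02 and 0.08, the Kaplan-Meier difference between arms is 61.7 − 21.3 = 40.4 points. The cumulative-incidence difference is 32.5 points under HR 0.6 and 46.9 under 88% PFS. The curve can therefore overstate or understate the contrast.

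**Step 3: which arm is affected more?** Take 78 pairs of improvement hazards between 0.01 and 0.12, with ibrutinib at least as fast as ofatumumab. Under HR 0.6 the absolute excess was larger for ofatumumab in 50% of pairs at 6 months, 55% at 12 and 64% at 24. Under 88% PFS it was larger for ofatumumab in all of them. In relative terms it was larger for ofatumumab in every pair under both proxies.

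**The case against.** The strongest reply is that the plan never says deaths are censored. A patient who dies without improving can be kept at risk to the data cut-off, and one minus Kaplan-Meier then tracks the cumulative incidence. Protocol section 12 leaves detail to the SAP, and the only SAP supplied is for the final analysis, so a rule may exist in a plan for the primary analysis that is not among the documents. This stands as a limit: censoring is an inference from ordinary practice. It does not remove the gap, because the text as written leaves open a choice worth several points.

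Three stronger readings are tempting, and the documents do not support them.

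- *A reader might infer that the trial's share improved is overstated.* That share is a raw percentage with a chi-square test. Censoring does not enter it, and no Kaplan-Meier landmark is prespecified for this endpoint.
- *A reader might infer that the bias falls mainly on ofatumumab.* That rests on pairing the 5.8-month and 88% proxies, which implies a hazard ratio of 0.0107/0.1195, about 0.09, where the design assumes 0.6. The proxies also come from different studies, and the ofatumumab figures come from refractory disease, whereas this trial also admits patients after one prior therapy.
- *A reader might infer that progression ends observation in the same way as death.* Appendix M keeps counts going for ofatumumab patients on next-line ibrutinib, and progression does not preclude improvement. Treating it as a competing event is a choice of estimand, so the larger figures in Step 2 are conditional on that choice.

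**Conclusion.** The point holds in a limited form. Protocol 12.8.2.4 names Kaplan-Meier for an event that death precludes and gives no rule for death. If deaths are censored, the curve is too high in both arms. In the control arm the 12-month excess is about 7 to 12 points, assuming constant independent hazards, a median survival of 14.5 months borrowed from a refractory population, and Kaplan-Meier values of 30 to 60%. The documents give no survival figure for ibrutinib from which to compute the matching death-only excess, and in absolute points the excess need not be larger for ofatumumab.

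The damage is confined to the descriptive curve and any median or landmark read from it. The log-rank test still compares cause-specific hazards validly. The primary endpoint, alpha and event count are not involved. The final-analysis SAP drops the time-to-event version, so the point concerns only outputs produced under 12.8.2.4.

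A second gap is whether improvement after progression or after crossover counts. Analysis as randomised would credit it to the ofatumumab arm by default, but nothing says so. The SAP limits response rate to the period up to subsequent therapy and states no such limit for the hemoglobin and platelet rows.

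**What to change.** In Protocol 12.8.2.4, replace the Kaplan-Meier summary with the Aalen-Johansen cumulative incidence of sustained improvement by arm, with death as a competing event. Keep the unstratified log-rank test and label it a comparison of cause-specific hazards. Leave the percentage and its chi-square test as they are.

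Add one sentence saying whether improvement after progression, or after crossover to next-line ibrutinib, counts toward the endpoint. If it does not, treat those as competing events too. Apply the same rule to any existing table or figure of this endpoint.

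The cost is a short text change and one re-run on data already held. The reported percentages improved over time will be somewhat lower, and a median may no longer be reached.
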